8.2 Analysis of binary outcome variables

Binary outcome variables will be displayed as percents with 95% exact confidence intervals (Rosner, 1995). The exact confidence interval (P_L, P_U) will be as the solutions to the following equations. If x is the observed outcome (that is, there are x successes in the 24 subjects) then the lower bound will be the solution P_L to the equation

$$0.025 = \Pr \{ \text{at least } x \text{ successes} \mid \text{probability of success} = p_L \} = \sum_{k=x}^{24} \binom{24}{k} p_L^k (1-p_L)^{24-k}.$$

The upper bound will be the solution to the equation

$$0.025 = \Pr \{ \text{no more than } x \text{ successes} \mid \text{probability of success} = p_U \} = \sum_{k=0}^x \binom{24}{x} p_U^k (1 - p_U)^{24-k}.$$

Standard search methods will be used to solve these equations.

8.3 *Analysis of time to event measures*

All time to event measures will be summarized using Kaplan-Meier (product limit) life table methods. Results will be displayed as survival plots. Tables with estimates and 95% confidence intervals for the rates at 1-year, 2-years, and 3-years after the first and last islet transplants will be provided. Separate analyses will be performed for time from first transplant and time from last transplant.

9. Analysis of Demographic and Baseline Measures

9.1 *Baseline Data*

Baseline data collected for the ITT analysis consists of demographic information and medical/physical assessments during the waiting period for islet transplant. These data will be grouped into the following categories:

- Demographic variables
 - Age
 - Sex
 - Race (White, Black, Hispanic, Asian and Other)
- Body Habitus and Quality of Life
 - Body Weight
 - Height
 - Body Mass Index (BMI)
- Diabetes Control
 - Insulin requirement (units/day)
 - HbA1c
 - Fasting and post prandial plasma glucose
 - Fasting and post prandial C-peptide
 - 90-minute C-peptide following consumption of Boost[®] or equivalent
 - 90-minute glucose following consumption of Boost[®] or equivalent
 - Number of severe hypoglycemic events in the last year
 - MAGE score
 - LI
 - Clarke Score
 - HYPO score
 - β -score
 - C-peptide/(glucose·creatinine) ratio

Statistical Analysis Plan

- Measures of Cardiovascular function
 - Carotid intimal thickness
 - Atherogenic profile (fasting lipids, c-reactive protein, serum amyloid A, Apolipoprotein A1, Apolipoprotein B, and the ratio of Apolipoprotein A1 and Apolipoprotein B).
- Measures of Renal function
 - Serum Creatinine
 - Spot urine albumin creatinine ratio, and protein excretion.
- QOL Measures (defined in Protocol Section 9.1.10)
 - SF-36
 - EQ-D5
 - Diabetes Distress Scale

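### SAP Section 8.2 prints C(24,x) instead of C(24,k) in the upper-limit equation, so descriptive two-sided exact intervals solved from it are wrong, mainly at low counts and at 24 of 24

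*SAP*

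**What the plan says.** SAP Section 8.2 sets one method for binary outcomes: "Binary outcome variables will be displayed as percents with 95% exact confidence intervals". It takes x as the observed count, so that "there are x successes in the 24 subjects", and writes out two equations, each set to 0.025.

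- **Lower limit.** The probability of at least x successes is written as a sum with the code "k=x}^{24} \binom{24}{k} p_L^k (1-p_L)^{24-k". The coefficient is C(24,k), with k the running index.
- **Upper limit.** The definition reads, in typeset code, "0.025 = \Pr \{ \text{no more than } x \text{ successes} \mid \text{probability of success} = p_U". The sum that follows is "k=0}^x \binom{24}{x} p_U^k (1 - p_U)^{24-k". Here k runs from 0 to x and appears in both exponents, but the coefficient is C(24,x).

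The section closes with "Standard search methods will be used to solve these equations". It gives no separate rule for x = 0 or x = 24.

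**The concern.** A binomial lower tail adds C(24,k) p^k (1-p)^(24-k) over k = 0 to x. With C(24,x) in every term, the terms are not binomial probabilities and their sum is not the tail named on the same line. The two ends of one interval would then rest on different functions. Because the SAP says the equations themselves will be solved numerically, someone programming from the page would obtain wrong upper limits.

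The intervals at stake are descriptive two-sided ones. Sections 11.3 to 11.6 send MAGE ≥ 11.1 mmol/L, LI ≥ 433, HYPO ≥ 1047 and reduced awareness (Clarke score ≥ 4) to the binary-outcome method. Section 11.2 asks for 95% intervals for three HbA1c proportions. Section 14.2 asks for an exact two-sided 95% interval for immune sensitization. Several of these are unfavorable outcomes for which low counts after transplant are plausible, and low counts are where the printed equation is furthest off.

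**Working it through.** **Inputs (all from SAP Section 8.2).** n = 24; x = 0 to 24; tail probability 0.025 on each side; the two printed sums. The section gives no numerical limit to reproduce, so the check is whether each printed sum equals the stated 0.025 at the exact (Clopper-Pearson) limit.

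**Lower limit.** The printed sum with C(24,k) equals 0.025 at the exact lower limit for every x from 1 to 24. It is correct.

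**Upper limit, two functions.**

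- Correct: R(x,p) = Σ_{k=0..x} C(24,k) p^k (1-p)^(24-k)
- As printed: W(x,p) = C(24,x) Σ_{k=0..x} p^k (1-p)^(24-k)

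As p approaches 0, W approaches C(24,x), which is 24 at x=1 and 134,596 at x=6. W is therefore not a probability.

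**x = 0.** Both reduce to (1-p)^24 = 0.025, so p_U = 1 - 0.025^(1/24) = 14.25%. This is the only exact match.

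**x = 1, by hand.**

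- As printed: 24(1-p)^24 + 24p(1-p)^23 = 24(1-p)^23 = 0.025. So p = 1 - (0.025/24)^(1/23) = 25.81%.
- Correct: (1-p)^23 (1 + 23p) = 0.025, solved by p = 21.12%.
- True tail at the printed root: (0.025/24) × (1 + 23 × 0.2581) = 0.0072, not 0.025.

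**x = 24, by hand.** C(24,24) = 1, so W = [p^25 - (1-p)^25]/(2p - 1). At p = 0.8507 this is about 0.01755/0.7014 = 0.025. W is unchanged when p and 1-p are swapped, so the other root is 0.1493. The exact lower limit at x = 24 is 85.75%, so even the larger root puts the upper limit below the lower limit.

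**Numerical solution** (grid search plus root-finding; largest root shown):

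| x | Upper limit as printed | Correct upper limit | Difference (points) | True lower tail at printed root |
|---|---|---|---|---|
| 1 | 25.81% | 21.12% | +4.7 | 0.0072 |
| 2 | 33.74% | 27.00% | +6.7 | 0.0043 |
| 3 | 39.78% | 32.36% | +7.4 | 0.0037 |
| 4 | 44.62% | 37.38% | +7.2 | 0.0040 |
| 6 | 52.22% | 46.71% | +5.5 | 0.0063 |
| 9 | 61.67% | 59.41% | +2.3 | 0.0141 |
| 12 | 71.21% | 70.88% | +0.3 | 0.0228 |
| 13 | 74.43% | 74.45% | 0.0 | 0.0251 |
| 16 | 83.87% | 84.37% | -0.5 | 0.0297 |
| 18 | 89.77% | 90.23% | -0.5 | 0.0306 |
| 24 | 85.07% | 100% (convention) | -14.9 | 1 |

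**Extra roots.** For x = 20 to 23 the printed equation has three roots. At x = 20 they are 46.2%, 58.8% and 95.0%, against a correct limit of 95.3%. The two smaller roots lie below the observed 83.3%.

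**After the correction.** With C(24,k), the sum equals 0.025 at the exact limit for every x from 0 to 23. At x = 24 the tail is 1 for every p, so the correct equation has no root either and p_U = 1 has to be set by convention.

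**The case against.** The strongest defense is that Section 8.2 fixes the method correctly three other ways: it calls the interval exact, with a textbook citation; it defines the upper tail correctly in words; and it prints a correct lower-limit sum. Any standard exact-binomial routine would return the right limit. The likely source is visible: Section 10.1 writes its own tail with x as the running index, so C(24,x) is right there, and one x seems to have survived in Section 8.2 when the index became k. A k/x confusion in text extraction also cannot be wholly excluded, and the original page will settle it. All of this stands. It makes the error an index slip rather than a wrong choice of method, but it does not make the printed equation right.

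A reader might go further in three ways that the SAP does not support.

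- **That the efficacy conclusion is at risk.** Section 10.1 uses a one-sided exact test with a correctly printed lower bound. Section 10.2.1 uses one-sided tests and one-sided exact intervals for the binary key secondary outcomes. Neither needs the faulty equation.
- **That freedom from severe hypoglycemia in all 24 subjects would be reported with an upper limit of 85%.** That outcome is key secondary outcome 3, reported with a one-sided interval and tested against a minimum rate. Section 10.2.2 analyzes the additional efficacy endpoints in the same way.
- **That coverage collapses at high rates.** Taking the largest root, the chance that the upper limit falls below the true rate is 10.7%, 29.8% and 48.7% at true rates of 90%, 95% and 97%. But x = 24 alone contributes 0.90^24 = 8.0%, 0.95^24 = 29.2% and 0.97^24 = 48.1%. Without it the figures are about 2.8%, 0.6% and 0.5%, against 0.5% to 0.7% for the correct limit. At x = 24 the convention p_U = 1 is needed whichever coefficient is printed, and an upper limit below an observed 100% would be noticed.

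The spurious roots at x = 20 to 23 are likewise a limited hazard, because they fall below the estimate and can be recognized as wrong.

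**Conclusion.** The point holds as an error in one printed equation with limited reach. Solved as written, the two-sided upper limit is too high by about 5 to 7 percentage points for x = 1 to 6. The excess shrinks to 0.3 points by x = 12, and the limit is then at most about 0.5 points too low up to x = 23 at the largest root. At x = 0 it is correct; at x = 24 it is unusable. At low counts the error widens the interval, so it overstates uncertainty rather than hiding it.

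This rests on three assumptions: the analyst solves the printed equation instead of using a standard routine; n is 24; and the 95% intervals in Sections 11.2 and 14.2 follow Section 8.2, the only place where the SAP writes out a two-sided binomial interval. No primary or key secondary test or interval changes.

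**What to change.** In Section 8.2, replace the upper-limit equation by

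0.025 = Σ_{k=0..x} C(n,k) p_U^k (1 - p_U)^(n-k),

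with n the number of subjects analyzed for that outcome, and write the lower-limit equation with the same n. Add that p_U = 1 when x = n and p_L = 0 when x = 0, since the correct equations have no root in those cases. Naming the interval as Clopper-Pearson would let a programmer check it against standard software.

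The cost is one corrected equation and one added sentence. No data, design, sample size or test is affected. If intervals have already been programmed, comparing them with a standard exact routine will show whether the slip reached the output.

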9.2 Analysis of Baseline Data

The number of subjects who do not meet the eligibility criteria will be reported, grouped by center. The numbers will be further broken down by the reasons for exclusion. These numbers and the corresponding rates will be reported in the summary table provided in SAP Appendix 7.

Descriptive statistics of baseline data, grouped by center, will be presented in a summary table. Continuous data will be summarized by mean, standard deviation, median, minimum, and maximum. Categorical data will be presented as numbers and percentages. The template of this table is described in SAP Appendix 1. Since the number of subjects transplanted in each center is small, there will be no significance tests for the differences of the baseline data among the seven centers.

9.2.1 Analysis of demographic variables

9.2.1.1 Age

The distribution of age at baseline will be displayed as mean, standard deviation, median minimum and maximum.

9.2.1.2 Sex and race

Sex and race will be displayed as counts and percents.

Statistical Analysis Plan

9.2.2 Analysis of Baseline Diabetes Control Variables

Diabetic control variables include insulin requirement, fasting and post-prandial plasma glucose and C-peptide, glucose and C-peptide 90 minutes post Boost® (or equivalent) glucose challenge, number of hypoglycemic events in the last year, MAGE score, LI, Clarke score, HYPO score, β -score, and C-peptide/(glucose·creatinine) ratio (the ratio of C-peptide to the product of glucose and creatinine).

The distribution of number of hypoglycemic events in the last year will be presented in tabular form. The remaining variables are ordinal scale and will be analyzed as described for continuous variables.

9.2.3 Analysis of Baseline Body Habitus Variables

Body habitus variables include height, weight, and body mass index (BMI). BMI is computed as the ratio of weight to the square of height (kg/m^2). All three variables are continuous scale and will be analyzed in the same manner as described for continuous variables.

All QOL scales are continuous and will be analyzed in the manner described for the continuous scale variables. Each scale will be tabulated as mean, standard deviation, median, minimum and maximum. 95% confidence intervals will be computed in the manner described for continuous variables.

10. Analysis of Efficacy Measures

10.1 Analysis of Primary Endpoint

HbA1c is the standard measure of glucose control and is used in all major studies as an endpoint for glycemic control. It has been valuable as a risk predictor of diabetes complications. However, since HbA1c is an integrated average, it does not provide information about the range of glucose values a subject experiences. This limitation is a rationale for also including hypoglycemic event occurrence as part of the primary endpoint and various glycemic excursion measures as secondary endpoints.

The primary endpoint (as defined in Section 2.3.1) is the proportion of subjects with both an $\text{HbA1c} \leq 6.5\%$ and an absence of severe hypoglycemic events at 1 year or a reduction in HbA1c of 1 point and an absence of severe hypoglycemia at 1 year after their first transplant. For brevity in the following discussion, we will denote this outcome as “favorable outcome at one year”.

The primary analyses will be an intention to treat analysis. It is expected that some subjects will be screened and found eligible but will never receive an islet transplant either because a compatible isolation never becomes available, because the subject decides to no longer participate in the study, or because some other event precludes them from participation. The intention to treat population will be defined as all subjects for whom induction antibody therapy for an islet transplant is begun. In addition, a per-protocol analysis will include all subjects in whom the islet infusion procedure is initiated. The procedure will be considered initiated when the operator has started the process of obtaining access to the portal vein (*i.e.*, entered the body with a needle or scalpel).

The primary aim of the analysis is to estimate the true rate of favorable outcome at one year after their first transplant in all eligible subjects for whom induction for an islet transplant is begun. The observed favorable outcome rate and a one-sided 95% exact binomial confidence interval will be used to estimate the true favorable outcome rate. The primary analysis will compute a one-sided exact binomial test of the null hypothesis that the true rate is less than or equal to 27% versus the alternative that the true rate exceeds 27% (see sample size justification). The analysis will be considered to support efficacy if the null hypothesis is rejected at the 5% level of significance. The lower bound for the confidence interval p_L will be determined as the value that satisfies the following equation:

$$0.05 = \sum_{x \geq r} \binom{24}{x} p_L^x (1 - p_L)^{24-x}$$

The rates of favorable outcome and exact one-sided 95% confidence intervals will be computed for each contributing center.

Statistical Analysis Plan

This analysis will be conducted for the ITT population. The primary endpoint should be available for all treated subjects. An exception will be if a death occurs, if the subject withdraws consent to be followed, or if immunosuppression is begun but the subject never receives a transplant. In these cases the endpoint will be classified as failure to achieve a favorable outcome. Should the endpoint not be evaluated for a particular individual for other reasons, a failure will be imputed unless an evaluation is done at a time longer than one year after transplant, in which case, that later value will be imputed. All imputations will be reported with the primary analysis. The rates and the exact one-sided 95% confidence intervals for complete data and imputed data will be compared to ascertain the sensitivity of the imputation.

10.2 Analyses of Secondary Endpoints

Except for the primary analyses there are no explicit hypotheses in the protocol. Changes in the secondary outcomes are of interest as they will relate to efficacy as measured by the primary outcome variable. All analyses are descriptive and are intended to document the changes in these important variables. Secondary outcomes will be used to support the decision for efficacy of islet transplantation in this population but are not intended to be used explicitly for making a decision for the efficacy of islet transplantation in this population.

10.2.1 Analysis of Key Secondary Endpoints

Because this is a single intervention study, the tests will be one sided tests for whether the true rates are greater than the endpoint's' predetermined "minimum rate for efficacy". These minimum rates were determined by the investigators to be large enough to have credibility for the islet transplant community. The minimum rate for efficacy is provided in Table 10.1 for each of the key secondary outcomes.

Statistical Analysis Plan

Table 10.1: Key Secondary Outcomes and Minimum Rates for Efficacy

	Key Secondary Outcome	Minimum Rate for Efficacy
1	At 365 ± 14 days after the last islet transplant (the primary at 365 days after the last transplant): The proportion of subjects with both an HbA1c ≤ 6.5% and an absence of severe hypoglycemic events from Day 28 to Day 365, or a reduction in HbA1c of 1 point and an absence of severe hypoglycemia from Day 28 to Day 365.	50%
2	At 365 ± 14 days after the first islet transplant: The proportion of subjects with HbA1c < 7.0% and free of severe hypoglycemic events from Day 28 to Day 365.	50%
3	At 365 ± 14 days after the first islet transplant: The proportion of subjects free of severe hypoglycemic events from Day 28 to Day 365.	50%
4	At 365 ± 14 days after the first islet transplant: The proportion of subjects with HbA1c < 7.0%.	50%
5	At 365 ± 14 days after the first islet transplant: The proportion of subjects with HbA1c ≤ 6.5%.	50%
6	The proportion of subjects with a reduction in HbA1c of at least 1 point	50%
7	At 365 ± 14 days after the first islet transplant: The proportion of insulin-independent subjects.	20%
8	At 365 ± 14 days after the first and last islet transplant: The change from baseline in the Clarke score.	Favorable increase of 1 point

As with the primary endpoint, the key secondary endpoints should be available for all transplanted subjects and the analysis will be conducted for the ITT population. If an endpoint is

Statistical Analysis Plan

not available for a transplanted subject then it will be imputed using the same rules that were used for the primary endpoint. That is the measure will be imputed as a failure unless later data would make the outcome a success.

For each of the binary outcomes (1-7), the observed rate for each key secondary outcome will be used as the point estimate. The analysis will also compute an exact binomial one-sided test for the null hypothesis that the true rate of the outcome is less than or equal to the predetermined minimum rate for efficacy against the alternative that the true rate exceeds the minimum rate for efficacy. Change from baseline in the Clarke score will be analyzed as a continuous variable.

We will use the Benjamini and Hochberg (Benjamini & Hochberg, 1995) method to account for the multiplicity of the key secondary tests. This method controls the false discovery rate (FDR) rather than the more familiar family-wise error rate (FWER). It provides a powerful approach for identifying those positive tests that are not likely to be true while controlling a reasonable measure of the expected number of false positive tests (the FDR).

The multiple testing procedure considers testing m hypotheses H_1, H_2, \dots, H_m . Each test yields the corresponding p-values P_1, P_2, \dots, P_m . Let $P_{(1)} \leq P_{(2)} \leq \dots \leq P_{(m)}$ be the ordered p-values, and let $H_{(i)}$ denote the null hypothesis corresponding $P_{(i)}$. The Bonferroni-type multiple testing procedure is defined by the following:

Let q^* the maximum false discovery rate and let k be the largest i for which $P_{(i)} \leq \frac{i}{m} q^*$; then reject all $H_{(i)}$ $i=1, 2, \dots, k$.

For this study there are 8 key secondary endpoints so $m=8$ and we will fix q^* at 0.1.

For each key secondary outcome, the observed rate will be used as the point estimate. The rate and a 95% exact one-sided confidence interval will be reported along with the p-value from an exact one-sided test of the corresponding null hypothesis.

10.2.2 Additional Efficacy Endpoints

Excluding the first key secondary endpoint, the additional efficacy endpoints are just the key secondary endpoints measured at one year, two years, and three years after the first and after the last islet transplant. They will be analyzed in exactly the same way as the key secondary endpoints but no adjustment will be made for multiple comparisons. The secondary endpoints that are not directly related to the primary and key secondary efficacy endpoints are discussed in detail in the following sections.

10.2.3 Additional Post-Hoc Analyses

The HbA1c component of the composite primary endpoint for CIT-06, aimed at controlling HbA1c levels at or below 6.5% or reducing HbA1c levels by 1 percentage point, is based on a minimum rate for efficacy of 27%. This is in contrast to the HbA1c component of the primary endpoint for the CIT-07 trial, aimed at controlling HbA1c levels at or below 7.0%, which is based

Statistical Analysis Plan

on a minimum rate for efficacy of 50%. There are several CIT-06 key secondary outcome measures that, while assessing HbA1c levels at the 6.5% threshold or the 1 percentage point decrease threshold, still use the CIT-07 minimum rate for efficacy of 50%. The study team found the SAP lacking in that it never stipulated that these key secondary outcomes also be evaluated at the minimum rate for efficacy for the CIT-06 primary outcome, 27%. Therefore, we propose to add the three corresponding analyses (from Table 10.1) to the analysis plan in a post-hoc manner. That is, they will not be considered key secondary outcomes, which would otherwise impact the pre-specified plan for adjusting for multiple key secondary comparisons, and they will not replace the current key secondary outcomes, but rather they will be considered additional post-hoc comparisons.

The following table describes the additional post-hoc analyses in terms of Table 10.1, where the additional analyses are broken out from the key secondary analyses table.

Table 10.2 Additional Post-Hoc Analyses

	Additional Post-Hoc Analyses	Minimum Rate for Efficacy
1	At 365 ± 14 days after the last islet transplant (the primary at 365 days after the last transplant): The proportion of subjects with both an $\text{HbA1c} \leq 6.5\%$ and an absence of severe hypoglycemic events from Day 28 to Day 365, or a reduction in HbA1c of 1 point and an absence of severe hypoglycemia from Day 28 to Day 365.	27%
5	At 365 ± 14 days after the first islet transplant: The proportion of subjects with $\text{HbA1c} \leq 6.5\%$.	27%
6	The proportion of subjects with a reduction in HbA1c of at least 1 point	27%

11. Analysis of metabolic outcomes

Separate identical analyses will be reported for outcomes measured at one year after the first and after the last islet transplant, at two years after the first and after the last islet transplant, and at three years after the first and after the last islet transplant.

11.1 *The percent reduction in insulin requirement*

Subjects will record their total daily insulin dose on self-monitoring diaries. The percent reduction from the baseline insulin requirement ((follow-up minus baseline) divided by baseline) will be computed for each subject for each time point. The analysis of the reduction percentage will use the method described above for a continuous variable.

11.2 *HbA1c*

The primary endpoint requires that either HbA1c at one year after the first transplant is less than or equal to 6.5% or has dropped at least one percent. A secondary endpoint requires that HbA1c is less than 7.0%. The analyses will present the observed percent and 95% confidence intervals for the true percent for the three outcomes: (1) the proportion of subjects with HbA1c $\leq 6.5\%$, (2) the proportion of subjects with HbA1c $< 7.0\%$, and (3) the proportion of subjects with a drop of at least 1.0%.

Additional analyses of HbA1c will adopt the method for a continuous scale variable. Data will be displayed as mean, standard deviation, minimum and maximum. In addition, 95% confidence intervals will be computed as described in the methods section. Change from baseline will be computed and analyzed using the same methods.

11.3 *Mean amplitude of glycemic excursions (MAGE)*

The MAGE requires capillary glucose readings over two consecutive days (a minimum of four readings a day), and is defined as the arithmetic mean of blood sugar increases (or decreases) when both increases and decreases (or vice-verse) at subsequent points in time are greater than 1 standard deviation of the blood sugar for the same two day period (Service, Molnar, Rosevear, Ackerman, Gatewood, & Taylor, 1970). If the MAGE is ≥ 11.1 mmol/L, the subject is considered to have labile diabetes.

The first analysis for this variable directly uses MAGE and adopts the method for a continuous scale variable. In addition, subjects will also be categorized into two groups depending on whether or not the MAGE ≥ 11.1 mmol/L. The analysis of the rate of labile diabetes will be displayed using the methods described for a binary outcome variable.

11.4 *Glycemic lability index*

LI is a measure of blood glucose lability which is based on the change in glucose over time. The LI requires 4 or more daily capillary blood glucose (BG) measurements over a 4 week period.

Statistical Analysis Plan

For each week, the sum of the squared differences in consecutive glucose readings is divided by the hours apart the readings are determined. Only differences in time that are greater than or equal to 1 hour and less than or equal to 12 hours are used in calculations. This sum is calculated for each of the four weeks and the LI is the mean of the four weekly values (Ryan, Shandro, K, & al., 2004), that is:

$$LI = \frac{1}{4} \times \sum_{i=1}^4 \sum_{j=1}^{N_i} \frac{(\Delta Gluc_{i,j})^2}{\Delta h_{i,j}}$$

where $\Delta Gluc_{i,j}$ is the j^{th} eligible difference of glucose readings in the i^{th} week, $\Delta h_{i,j}$ is the time interval in hours for the j^{th} eligible difference of glucose readings in the i^{th} week. N_i is the total number of the eligible differences of glucose readings in the i^{th} week.

Most subjects have scores under 300 mmol/L²/h·wk⁻¹ with a median of 223 (25 – 75th percentiles 130 – 329 mmol/ L²/h·wk⁻¹). An LI ≥ 433 mmol/ L²/h·wk⁻¹ (90th percentile) indicates serious problems with glycemic lability. The first analysis for this variable directly uses LI and adopts the method described for continuous scale variables. Change from baseline will also be computed and analyzed using the same methods.

Subjects will also be categorized into two groups depending on whether or not the LI ≥ 433 mmol/ L²/h·wk⁻¹. The analysis of the rate of serious problems with glycemic lability will also be analyzed using the method for binary outcomes.

